Study protocol and Statistical Analysis Plan

Clinical evaluation of sphygmomanometer BN1(Bionet BNiBP module) according to ISO 81060-2:2018 protocol

Clinical Research Ethics Review Committee :

Hanyang University Seoul Hospital IRB(Institutional Review Board)

(IRB File No. HYUH 2020-02-034)

Principal Investigator : [name]

[name], [contact]

December 7th, 2020

Hanyang University Seoul Hospital

Department of Family Medicine

[name]

Index

1. Name and address of the clinical trial institution	3
2. Purpose and background of clinical trials	3
3. Medical device information for clinical trials	3
4. indication	7
5. Research period	7
6. Method of clinical trial	7
6-1. Study subjects	7
6-2. Research method overview	9
7. Observation items, clinical examination items, and observational examination methods	13
8. References	16

1. Name and address of the clinical trial institution

Department of Family Medicine, Hanyang University Seoul Hospital /
[name]

2. Purpose and background of clinical trials

A blood pressure monitor is a basic medical device that is essential for diagnosing cardiovascular diseases, and its importance is very high. Most of the electronic sphygmomanometer equipment or modules (components) used in Korea are foreign products. Recently, a new electronic sphygmomanometer module was developed by Bionet, a domestic company, and has been approved by the Ministry of Food and Drug Safety and is being applied to clinical practice. In order for a blood pressure monitor to be used as a medical device for diagnosis of various diseases, it is important to test the accuracy of blood pressure to know the exact degree of blood pressure measurement. In this study, a clinical study was conducted to investigate the performance of the equipment using the auscultation method used as a reference (gold standard) for non-invasive blood pressure measurement (NIBP) at the Department of Family Medicine at Hanyang University Hospital and the newly developed equipment at the same time. We want to help the industry.

3. Medical device information for clinical trials

3-1. Medical device in test

- Name/code name of drug/device/procedure method: BM5 with BN1 (BNiBP) (Bionet Co., Ltd., Korea)
- Item name: Patient monitoring device
- Purpose and efficacy: Displays biometric information such as electrocardiogram (ECG), non-invasive blood pressure (NIBP), invasive blood pressure (IBP), body temperature (TEMP), blood oxygen saturation (SPO2), and respiration (RESP) on the screen. It is a monitoring device that analyzes blood pressure values during vital sign measurement and displays Systolic Blood Pressure (SBP) and Diastolic Blood Pressure (DBP).

Clinical Evaluation of Bionet Sphygmomanometer Module BN1 Based on ISO 81060-2:2018 Protocol

ClinicalTrials.gov ID: NCT06609486

- Other functions of BM5 are disabled and only the performance of NIBP function is evaluated.

- Cuff Specification and Method

Cuff Type	A Cuff (V0014C)	B Cuff (V0013C)	C Cuff (V0012C)
Pictures			
Available arm circumference range	27.5 ~ 36.5 cm	20.5 ~ 28.5 cm	13.8 ~ 21.5 cm

Pictures	Explanation
	
- The cuff is wrapped around the arm of the subject to be measured.

	
- When you press the NIBP operation button of the BM5, blood pressure measurement starts automatically.-(If necessary) If you press the NIBP operation button while measuring blood pressure, blood pressure measurement is stopped.
	
- When blood pressure measurement is finished, the result value is displayed at the bottom of the BM5 screen.

3-2. Auscultational measuring tool to be used as a reference

- 2 stethoscopes (connected to Y-piece or T-piece):

Pictures	Explanation
	
 - Product Name: Littmann Classic 2 - Manufacturer : 3M Littmann - Connect two stethoscopes with a T-piece so that two nurses required by the protocol can measure simultaneously.

- Aneroid sphygmomanometer :

Pictures	Explanation
	
 - Product Name: Greenlight 300 - Manufacturer: ACCOSON - Measurement method: non-mercury auscultation method

 - Shown to be compliant with the US standard for non-automated sphygmomanometers, ANSI/AAMI SP9:1994, and has been approved by the FDA (K040410). - It has also been shown to be compliant with the European standards EN1060-1, EN1060-2 and EN1060-3. - Approved by British Hypertension Society (www.dableducational.org) 	

- Hose

Pictures	Explanation
	
 - A hose from one cuff to both the electronic sphygmomanometer and auscultation sphygmomanometer - Length: 2M

- Cuff Specification

Cuff Type	A Cuff (V0014C)	B Cuff (V0013C)	C Cuff (V0012C)
Pictures			
Available arm circumference range	27.5 ~ 36.5 cm	20.5 ~ 28.5 cm	13.8 ~ 21.5 cm

4. Indication

Normal blood pressure/Attention blood pressure/Pre-hypertension/Hypertension

5. Research period

From IRB approval to October 31st, 2021

6. Method of clinical trial

6-1. Study subjects

[Selection Criteria]

- Subjects who have consented to participate in the clinical trial and voluntarily consented in writing
- Subjects who meet the criteria presented in ISO 81060-2:2018 Protocol 5.1 Subject requirements
 - Number : In order to evaluate the accuracy of the electronic blood pressure monitor, the number of study subjects should be at least 85.

: Unless otherwise specified, at least three valid blood pressure data pairs should be obtained from each study subject, and therefore the number of valid data pairs should be at least 255.

■ Gender distribution

: Male – more than 30%, Female – more than

■ Age distribution

: Bionet's NIBP module includes adults and children (Children: 3 to 12 years).

: Therefore, at least 35 children are included.

■ Limb size distribution

: Each cuff should be evaluated for at least $\frac{1}{2 \times c}$ of all subjects. (where c is the number of cuffs)

: At least 40% of personnel with arm circumferences greater than half of the measurable range specified on the cuff.

: At least 40% of personnel with arm circumferences less than half of the measurable range specified on the cuff.

■ Blood pressure distribution

: At least 5% of the reference SBP data must be less than or equal to 100 mmHg.

: At least 5% of the reference SBP data must be 160 mmHg or higher.

: At least 20% of the reference SBP data must be 140 mmHg or higher.

: At least 5% of the reference DBP data must be less than or equal to 60 mmHg.

: At least 5% of the reference DBP data must be 100 mmHg or higher.

: At least 20% of the reference DBP data must be 85 mmHg or higher.

[Exclusion criteria]

- Emergency surgery patient
- Subjects with psychiatric disorders such as mental retardation or autism
- Subjects whose blood pressure measurement is difficult or expected to be difficult
- Subjects who did not consent to the study

[Number of target subjects and basis for calculation]

- Number of target subjects
 - : According to ISO 81060-2:2018 5.1 Subject requirements, the number of NIBP subjects for adults and children should be 85 or more, including 35 or more children.
 - : Considering the dropout rate of 20%, 102 subjects (including more than 35 children) were recruited.
- Method of recruiting research subjects and obtaining consent
 - : Recruitment is made through the recruitment notice for patients and their guardians who visit Hanyang University Hospital. After giving a sufficient explanation in a language that the subject can understand and waiting for 15 to 30 minutes to understand the contents of the study, the principal investigator obtains written consent from the subject or his/her representative. In addition, we accept withdrawal from research participation at any time during the study participation period without loss of the research subject's refusal.
- Random assignment method and blinding method
 - : This clinical trial does not use randomization or blinding methods.

6-2. Research method overview

[Prepares]

- The auscultation-type blood pressure monitor used as a comparison target in accuracy evaluation must satisfy international standards.
- Prior to evaluating the accuracy of the electronic blood pressure monitor, two measurers should be trained to detect the same auscultation sound for each study subject.
 - e.g. British and Irish Hypertension Society: BP Measurement auscultatory tutorials
- Two measurers must undergo an audiogram hearing test.

[figure not shown]
[Measurement considerations]

- The auscultation method has the following sources of error and should be considered when measuring.
 - Improper combination of cuff size and arm width
 - The stethoscope or transducer is not positioned over the brachial artery
 - Measurer's hearing loss or incorrect technique
 - Fast cuff deflation

[Measurement method]

- Use the sequential measurement method.
- The test configuration comparing the accuracy of the electronic blood pressure monitor and the auscultation method blood pressure measurement is prepared to measure one arm of a subject at the same time using a Y-piece or a T-piece as shown in the figure. Since the exhaust speed of the automatic sphygmomanometer is fast and it is impossible to measure with the electronic sphygmomanometer and auscultate at the same time, a method of sequentially measuring the electronic sphygmomanometer and the auscultation method is taken.

EXAMPLES *Switching the power off and on, removing the BLOOD PRESSURE module and reinstalling it or issuing a reset command are methods to clear the memory of the previous DETERMINATION.*

- In the sequential measurement method, the procedure for measuring the reference value and the blood pressure of the test equipment is as follows.

First blood pressure measurement

1.	Reference blood pressure measurement by two observers	R0
2.	test medical device blood pressure measurement	T0

Blood pressure measurement to evaluate accuracy

3.	First reference blood pressure measurement by two observers	R1
4.	First test medical device blood pressure measurement	T1

5.	Second reference blood pressure measurement by two observers	R2
6.	Second test medical device blood pressure measurement	T2
7.	Third reference blood pressure measurement by two observers	R3
8.	Third test medical device blood pressure measurement	T3
9.	Fourth reference blood pressure measurement by two observers	R4

: Reference (R0 ~ R4) is the average value of the blood pressure measurement values

by auscultation method of two measurers.

: Measure R0 and T0 to check the function of the test medical device.

: Blood pressure measurement for accuracy evaluation. Measure in order of R1, T1, R2, T2, R3, T3, R4.

: Measure at least 1 minute apart.

: Each study subject has the following three data pairs.

T1 vs (R1, R2 mean), T2 vs (R2, R3 mean), T3 vs (R3, R4 mean)

■ Other

[figure not shown]
: If the reference SBP value of any two pairs is greater than 12 mmHg or the reference DBP value is greater than 8 mmHg, all data of the subject should be excluded.

: Despite these requirements, if the reference blood pressure of the subject does not meet the above criteria during the trial period, two consecutive pairs of reference blood pressure that meet the above criteria may be used.

: The number of study subjects using 2 pairs of reference blood pressure should be less than 10% of the number of study subjects using 3 pairs of reference blood pressure.

: If there are data to be excluded by both measurers (observers), additional measures are made, and up to 8 times per study subject is possible.

: To measure the circumference of the upper arm, with the forearm facing upward, and keeping the elbow angle at 90 degrees, measure the circumference at ④, the midpoint between ① and ②, as shown in the figure below.

: During the test, follow the American Heart Association (AHA) measurement guidelines below.

American Heart Association (AHA) measurement guidelines	
Recommend	Explanation
The patient sits comfortably on his back. Don't cross your legs. Arms are supported. The patient sits and rests for at least 5 minutes before measurement.	DBP is high in a sitting position, and SBP is high in a standing position. A non-recumbent position can increase DBP, and a cross-legged position can increase SBP. In the case of elderly patients, blood pressure in the sitting and standing state is periodically measured to differentiate orthostatic hypotension.
Arms should be supported at heart level. The meter is placed in the center of the sternum.	If the arm is lower than the right atrium, the blood pressure is measured too high, and if the arm is higher than the heart, the blood pressure is measured too low. If your arm is not supported, your blood pressure will be high.
The cuff wraps more than 80% of the patient's arm circumference.	A blood pressure cuff that is small relative to the patient leads to measurement errors, and a cuff that is too small leads to a deviation of 2 to 10 mmHg or more.
The mercury meter deflates at a rate of 2 to 3 mmHg per second.	When subtracting more than 2 mmHg per second, the SBP is lower than the actual value and the DBP is higher than the actual value.
Measure SBP and DBP at the first and last beating sounds, respectively.	Measures with an accuracy of up to 2 mmHg.
Neither the patient nor the measuring person should speak.	Deviations may occur in measurements. Just by listening, it rises above 10 mmHg.

	Factors causing deviations in measurement include exercise, smoking, drinking, muscle tension, bladder distension, room temperature, and ambient noise.
--	---

7. Observation items, clinical examination items, and observational examination methods

[Basic items]

- Date and time
- Clinical trial number & subject number
- date of birth
- age
- gender
- On antihypertensive medication
- arm circumference
- Pulse
- Cuff Size (A Cuff, B Cuff, C Cuff)

[Items excluded from clinical trials]

- Complete blood pressure range recruitment (Range complete)
- Arrhythmia
- Device failure
- Cuff size unavailable
- Poor quality of Korotkoff sounds
- Observers disagreement
- Other factors

[Record blood pressure readings]

- All blood pressure units are recorded in mmHg, and the measurement interval, including the time required for cuff replacement, should be at least 60 seconds. A separate sheet is used to record the study subject's running total according to the blood pressure range.

[Compare]

- It is evaluated by statistically comparing the blood pressure measured by the test medical device with the blood pressure measured by the auscultation method.

[Statistical analysis]

- For 85 or more study subjects, the following two criteria must be satisfied for more than 255 valid data pairs by measuring 3 times per subject with a test medical device and auscultation method.
 - Criterions 1
 - It is calculated separately for SBP and DBP, and the difference between the data pairs for n test medical devices and auscultation-type blood pressure measurement values of all subjects must satisfy the following conditions.
 - : The average value \bar{x}_n for the difference between the test medical device and the auscultation method blood pressure calculated according to Equation (1) should be within ± 5.0 mmHg.
 - : The standard deviation s_n of the data pair calculated according to Equation (2) should be within 8.0 mmHg.
 - : \bar{x}_n and s_n must be expressed in units of at least 0.1 mmHg.

$$\bar{x}_n = \frac{1}{n} \times \sum_{i=1}^n (p_{SUT_i} - p_{REF-sq_i}) \quad (1)$$

$$s_n = \sqrt{\frac{1}{n-1} \times \sum_{i=1}^n (x_i - \bar{x}_n)^2} \quad (2)$$

$p_{SUT_i} - p_{REF-sq_i}$: Difference between the i-th blood pressure data pair

i : Index to individual element

n : number of measurements

p_{REF-sq_i} : The i-th reference blood pressure measurement calculated according to equation (3)

$$p_{REF-sq_i} = \frac{1}{4} \times (p_{REF_{i,1}} + p_{REF_{i,2}} + p_{REF_{i+1,1}} + p_{REF_{i+1,2}}) \quad (3)$$

$p_{REF_{i,1}}$: i-th blood pressure reading by measurer 1

$p_{REF_{i,2}}$: i-th blood pressure reading by measurer 2

- Criterions 2

- For m study subjects, the standard deviation s_m of the average value of the difference between data pairs of each study subject calculated according to Equation (4) must satisfy Table 1 below.

$$s_m = \sqrt{\frac{1}{m-1} \times \sum_{j=1}^m (x_j - \bar{x}_n)^2} \quad (4)$$

$p_{SUT_i} - p_{REF-sq_i}$: Difference between the i-th blood pressure data pair

j : Index to individual element

m : Number of study subjects

x_j : Test medical device blood pressure measurement calculated according to Equation (5)

$$x_j = \frac{1}{d} \times \sum_{k=1}^d (p_{SUT_{j,k}} - p_{REF-sq_{j,k}}) \quad (5)$$

d : Number of measurements per subject

k : Index to individual element

$p_{REF-sq_{j,k}}$: Reference blood pressure calculated according to equation (6)

$$p_{REF-sq_{j,k}} = \frac{1}{4} \times (p_{REF_{j,k,1}} + p_{REF_{j,k,2}} + p_{REF_{j,k+1,1}} + p_{REF_{j,k+1,2}}) \quad (6)$$

Table 1. Averaged subject data acceptance (Criterions 2) in mmHg

\bar{x}_n	Maximum permissible standard deviation, s_m , as function of, \bar{x}_n mmHg									
	0.0	0.1	0.2	0.3	0.4	0.5	0.6	0.7	0.8	0.9
± 0	6.95	6.95	6.95	6.95	6.93	6.92	6.91	6.9	6.89	6.88
± 1	6.87	6.86	6.84	6.82	6.8	6.78	6.76	6.73	6.71	6.68
± 2	6.65	6.62	6.58	6.55	6.51	6.47	6.43	6.39	6.34	6.3
± 3	6.25	6.2	6.14	6.09	6.03	5.97	5.89	5.83	5.77	5.7
± 4	5.64	5.56	5.49	5.41	5.33	5.25	5.16	5.08	5.01	4.9
± 5	4.79	-	-	-	-	-	-	-	-	-

8. References

- [1] BS Alpert, Validation of the Welch Allyn Spot Vital Signs blood pressure device according to the ANSI/AAMI SP10:2002. Accuracy and cost-efficiency successfully combined. *Blood Press Monit.* 2007. 12(5): p.345-7.
- [2] Andrew C., et al, Validation of the Omron 705IT(HEM-759-E) oscillometric blood pressure monitoring device according to the British Hypertension Society protocol. *Blood Press Monit.* 2006 11(1): p.27-32
- [3] Guidelines for Accuracy Evaluation of Electronic Sphygmomanometers – KFDA Food and Drug Administration
- [4] O'Brien et al., European Society of hypertension international protocol revision 2010 for the validation of blood pressure measuring devices in adult, *BPM*, 2010, pp.23-38
- [5] Stergiou et al., A universal standard for the validation of blood pressure measuring devices: Association for the advancement of medical instrumentation/European Society of Hypertension/International Organization for Standardization (AAMI/ESH/ISO) Collaboration statement, *Journal of Hypertension*, 2018, 36(3), pp.472-478.

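### Minor: the recruitment target of 102 is said to allow for 20% dropout, but it covers a loss of only 16.7% of those recruited

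*Combined protocol and SAP*

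**What the plan says.** Section 6-1 (Study subjects) takes its minimum from the ISO standard: "the number of NIBP subjects for adults and children should be 85 or more, including 35 or more children". The selection criteria in the same section ask for three valid pairs per subject, and "therefore the number of valid data pairs should be at least 255".

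The recruitment figure follows under the heading on target numbers and their basis: "Considering the dropout rate of 20%, 102 subjects (including more than 35 children) were recruited".

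Section 7 (Statistical analysis) carries the minimum into the acceptance rule: "For 85 or more study subjects, the following two criteria must be satisfied for more than 255 valid data pairs". Section 6-1 words the pair count as a minimum of 255 and section 7 as more than 255. I use 255 as the floor, since one pair makes no difference here.

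The plan gives no inflation formula, no definition of dropout or its denominator, no source for the 20%, and no rule for replacing subjects who are lost.

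**The concern.** A dropout rate is ordinarily the share of those recruited who do not end with usable data. The losses that this plan foresees are of that kind. Subjects may withdraw at any time (section 6-1). All of a subject's data may be excluded when the reference readings vary too much (section 6-2). Subjects may also be lost to arrhythmia, device failure, poor Korotkoff sounds or observer disagreement (section 7). All of these come out of the number recruited, so 20% should be taken of 102, not of 85.

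If so, the only sample-size calculation in the plan contradicts the rate printed beside it, and the planned number is expected to fall below the plan's own minimum. No section says that recruitment goes on until 85 evaluable subjects are reached. The sheet described in section 7 keeps a "running total according to the blood pressure range", not a count against 85, and the research period in section 5 is "From IRB approval to October 31st, 2021".

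**Working it through.** **Inputs.** Minimum subjects 85 and minimum pairs 255 (sections 6-1 and 7); three pairs per subject (section 6-1); stated dropout rate 20% and stated target 102 (section 6-1). Significance level, power and effect size do not enter, because 85 is a minimum taken from the standard.

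**1. Reproduce the plan's figure.** Minimum × (1 + rate) = 85 × 1.20 = 102. This matches exactly, so 20% was added to the minimum.

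**2. Loss that 102 can absorb.** 102 − 85 = 17 subjects. As a share of those recruited this is 17/102 = 16.7%. Only as a share of the minimum is it 20% (17/85).

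**3. What remains at the stated rate.**
- Subjects: 102 × 0.80 = 81.6, short of 85 by 3.4.
- Pairs, if every subject gives three: 81.6 × 3 = 244.8, short of 255 by 10.2.

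**4. Target that matches 20%.** Minimum / (1 − rate) = 85/0.80 = 106.25, rounded up to 107. Check: 107 × 0.80 = 85.6, which is enough; 106 × 0.80 = 84.8, which is not. The gap is 107 − 102 = 5 recruits.

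**5. Other loss rates (assumed, since the plan gives no basis for 20%).**

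| Loss among recruits | Expected subjects left from 102 |
|---|---|
| 10% | 91.8 |
| 15% | 86.7 |
| 16.7% (17/102) | 85.0 |
| 20% | 81.6 |

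An expected shortfall arises only if the loss exceeds 16.7%.

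**6. Expectation is not assurance.** If each subject is lost independently with probability 20% (an assumption), the binomial chance of keeping at least 85 is about 24% with 102 recruits and about 61% with 107.

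**The case against.** The best defence is that the fault lies in the wording and not in the number. The plan does not define dropout, and adding 20% to 85 gives 102 exactly, so the authors may have meant over-recruitment by 20%. That may well be so, and it is why the preferred repair keeps 102. But the sentence calls the 20% a dropout rate, and no other section reconciles it with 102. It needs correcting on either reading. The past tense of the sentence does not change this: it stands under a heading on target numbers, and the rate and number disagree in any tense.

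The second defence is that little follows from it. Here the defence is right. The figure 102 feeds no power calculation or acceptance limit. The rule in section 7 begins "For 85 or more study subjects, the following two criteria must be satisfied", so the minimum binds whatever number was planned. A shortfall would be visible and could be made up by recruiting more. Section 7 also lists completion of a blood pressure range among its reasons for exclusion, which suggests that recruitment is steered by filled ranges rather than stopped at a fixed headcount. That is still not a rule to continue to 85.

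A reader might go further and infer three things that the documents do not support:

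- **That the accuracy results are compromised.** The number recruited does not bias the mean difference, s_n or s_m.
- **That the minimum of 35 children is also under-provided.** The plan recruits more than 35, which is a floor with no upper limit, so no shortfall can be shown.
- **That a promise to keep recruiting until 85 evaluable subjects are reached would settle the matter.** Section 6-2 lets some subjects contribute two pairs, provided they number less than 10% of those with three. With 78 three-pair and 7 two-pair subjects (7 is below 7.8), 85 subjects give 78 × 3 + 7 × 2 = 248 pairs, fewer than 255. Such a promise would also pass over the distribution requirements in section 6-1.

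**Conclusion.** The sentence is wrong as written, and the point is minor. The target is five short of the number that matches a 20% dropout rate; equivalently, the allowance is overstated, 20% against 16.7%. The conclusion rests on reading a dropout rate as a share of those recruited. The figure of about 245 pairs also assumes three pairs from every remaining subject. The effect is confined to planning: whether a shortfall occurs depends on the actual loss, and the minima of 85 subjects and 255 pairs apply in any case.

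**What to change.** Make the rate and the target in section 6-1 agree. Either of two wordings does it.

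1. **Keep 102 (preferred):** *102 subjects (20% more than the minimum of 85) will be recruited, which allows for a loss of up to 16.7% of those recruited.* This costs one reworded sentence and no extra subjects. The plan then states a smaller allowance than before.
2. **Keep 20%:** *Allowing for a dropout rate of 20% of those recruited, 107 subjects will be recruited (85/0.80 = 106.25).* This costs five more planned recruits. The text should say that 107 meets 85 on expectation only.

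A sentence on continuing recruitment is optional. If one is added, it should cover all of the plan's own minima: 85 subjects, 35 children, 255 valid pairs, and the section 6-1 requirements on sex, limb size and cuff, and blood pressure distribution. It should also say that it applies within the research period in section 5. A sentence tied to 85 subjects and 35 children alone should not be added.

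### Does the deflation-rate row of the measurement table, whose two cells disagree, bias the auscultatory reference enough to require a change?

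*Combined protocol and SAP*

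**What the plan says.** Section 6-2 closes its measurement instructions with "During the test, follow the American Heart Association (AHA) measurement guidelines below", followed by a table with a recommendation column and an explanation column.

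- The deflation row recommends: "The mercury meter deflates at a rate of 2 to 3 mmHg per second".
- The explanation in the same row reads: "When subtracting more than 2 mmHg per second, the SBP is lower than the actual value and the DBP is higher than the actual value".
- Under the measurement considerations in section 6-2, "Fast cuff deflation" is listed as a source of auscultatory error, without a rate.
- Section 3-2 describes the reference instrument this way: "Measurement method: non-mercury auscultation method".
- Criterion 1 in section 7 requires that the mean device-minus-reference difference "should be within ± 5.0 mmHg". Criterion 2 sets a ceiling on the between-subject standard deviation that falls as the mean difference grows (Table 1).

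No other readable text gives a deflation rate for the reference readings. Some figures in section 6-2 are not shown in the text available, so that statement covers the words only.

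**The concern.** The auscultatory reading is the yardstick for both acceptance criteria. If the plan tells observers to deflate at a rate that its own table calls too fast, the yardstick itself is off, and always in the same direction. Reference SBP would be too low, so device minus reference would move up. Reference DBP would be too high, so device minus reference would move down.

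The usual protections would not remove such a shift. Both observers listen through one T-piece to one deflation, so they share the error. Equation (3) averages four readings that can all err the same way. Collecting 255 or more pairs reduces random error but not a common shift. Depending on the device's own bias, the shift could help or hurt it.

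The row also speaks of a mercury instrument although the reference is not one, which suggests that the table was not adapted to this study.

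**Working it through.** **Comparing the two cells.** The recommended rates are 2 to 3 mmHg/s. The explanation places error at any rate above 2 mmHg/s. The overlap is every rate above 2 and up to 3, and only exactly 2 mmHg/s satisfies both cells. The inconsistency is real.

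**What a correction would do.** There are two possibilities, and the documents do not decide between them.

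1. The explanation is the slip. Correcting it changes a rationale and leaves every reading as it would have been.
2. The recommendation is the slip. Correcting it could change how the reference is read, so the size matters.

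**Size under the second possibility.** The documents give none. As an illustration, assume one sound per beat and a mean misreading of half the pressure drop per beat:

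mean error = 0.5 × rate × 60 / pulse

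| Pulse (/min) | 2 mmHg/s | 2.5 mmHg/s | 3 mmHg/s | Extra at 2.5 vs 2 | Extra at 3 vs 2 |
|---|---|---|---|---|---|
| 60 | 1.00 | 1.25 | 1.50 | 0.25 | 0.50 |
| 80 | 0.75 | 0.94 | 1.13 | 0.19 | 0.38 |
| 100 | 0.60 | 0.75 | 0.90 | 0.15 | 0.30 |

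As a share of the 5.0 mmHg limit, the extra error is 0.15/5.0 = 3% to 0.25/5.0 = 5% at 2.5 mmHg/s, and 0.30/5.0 = 6% to 0.50/5.0 = 10% at 3 mmHg/s. The table in section 6-2 puts reading accuracy at 2 mmHg, so the largest extra is 0.50/2 = one quarter of that. A faster pulse shrinks the figure: at 120/min the extra at 3 mmHg/s is 0.5 × 1 × 60/120 = 0.25 mmHg. That is relevant because at least 35 of the subjects are children aged 3 to 12.

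The model has no threshold at 2 mmHg/s. It gives 0.6 to 1.0 mmHg of error at exactly 2 mmHg/s, more than the 0.3 to 0.5 mmHg added by going to 3. It therefore gives an order of magnitude and does not represent the rule in the explanation cell.

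**Effect on Criterion 1.** Take the extreme shift of 0.5 mmHg. For SBP (shift upward), the decision on the mean can change only if the unshifted mean difference lies between 5.0 − 0.5 = 4.5 and 5.0 (wrongly failing), or between −5.5 and −5.0 (wrongly passing). DBP mirrors this. A constant shift leaves the standard deviation unchanged.

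**Effect on Criterion 2.** A constant shift leaves s_m unchanged but moves the ceiling read from Table 1:

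- mean 0.0 to 0.5: 6.95 − 6.92 = 0.03 mmHg lower
- mean 4.0 to 4.5: 5.64 − 5.25 = 0.39 mmHg lower
- mean 4.5 to 5.0: 5.25 − 4.79 = 0.46 mmHg lower

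The ceiling moves appreciably only when the mean difference is already close to its own limit.

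**The case for a change.** The strongest case for acting is that the plan makes the table binding, so its origin in a guideline does not excuse the conflict. Nothing in the readable text resolves it. The items to be recorded in section 7 include pulse and cuff size but not deflation rate, so the listed data would not show afterwards what was done. The shift has one direction and averaging does not remove it. Reconciling the row would cost very little.

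Most of that stands as description. The cells conflict, the direction of any error is as stated, and the rate is not among the listed data items. Three points keep it from becoming a change to the plan.

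- Asking for a rule that excludes every rate above 2 mmHg/s assumes that the explanation cell is right. The operative instruction is the recommendation. The other cell is rationale in a table labelled as a guideline and written in rough English throughout, so a wording slip there is quite possible, though not proven.
- Applying the row to this study's reference is a fair inference, since it is the only deflation rate given for auscultation. It is not stated, because the row names a mercury instrument.
- The neutral remedy, making the cells agree and naming the actual instrument, may touch explanatory text only and is not shown to alter any result.

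The plan also lists fast deflation among the errors to watch for and requires the two observers to be trained beforehand. Without a rate, that mitigates the gap but does not close it.

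**Conclusion.** No change to the design or analysis follows. One table row contradicts itself and misnames the instrument. Both are clerical matters to be reconciled in the wording, with no presumption about which cell is correct.

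No effect on the accuracy criteria has been shown. The illustrative worst case is 0.5 mmHg against a limit of ±5.0 mmHg. It rests on an outside model, a pulse of 60/min, every reading taken at 3 mmHg/s, and the recommendation being the faulty cell. Even then it bears on the result only for a device already near a limit. If the final report gives the deflation rate used, or says that it was not recorded, the reader has all that this point can offer.
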